## 1 BACKGROUND AND RATIONALE

**Diabetic nephropathy** (DN) is a common cause of end-stage renal disease (ESRD) and accounts for nearly half of all new patients starting dialysis in Singapore, the country with the highest rates of DN in the Asia-Pacific region. Despite the scale of the problem, little progress has been made in our understanding of the pathogenesis of the disorder and no new therapies have been offered.

## Renal glucose handling and the SGLT-2 inhibitors

The **SGLT-2 inhibitor** (SGLT-2i) class of drugs is a recently approved treatment for diabetes, which lower blood glucose levels by inhibiting renal reabsorption of glucose by SGLT-2 transporters in the proximal renal tubule, resulting in glucosuria.

## SGLT-2i and Diabetes Complications

Clinical trials of SGLT-2i in patients with type 2 diabetes (T2DM) have shown unexpectedly strong effects of the drug on diabetes complications. In the EMPA-REG OUTCOME trial, the SGLT-2i empagliflozin was able to i) reduce the risk of cardiovascular death and ii) slow the progression of DN in patients with diabetes. The effect of the drug on cardiac and kidney complications seems to be out of proportion to the modest glucose lowering ability of the drug. The reason for the protective effect on cardiac and kidney complications remains unexplained.

## SGLT-2i and Fuel Metabolism

Attempts to explain how SGLT-2i protect against diabetes complications have focused on several aspects of the drug's action including the effect on whole body fuel metabolism^6-8. The forced excretion of glucose in the urine leads to unique physiologic changes. Patients on the drug have lower glucose and insulin levels and raised glucagon. There is reduced glucose use, increased lipolysis with a resultant rise in fatty acid oxidation and ketogenesis. Interestingly, recent studies have also reported a rise in activity of the urea cycle. The net effect is a major shift in fuel metabolism away from glucose towards the burning of fat and ketone bodies. The shift in fuel metabolism is of particular interest given our recent findings of altered fuel metabolism in patients with diabetic nephropathy.

## Study aims

The aim of our proposed study is to **examine the state of fuel metabolism in patients with DN both before and after the use of SGLT-2i**. We anticipate that 30 days of treatment with the SGLT-2i empagliflozin will induce a shift in fuel metabolism in subjects with DN.

Our hypothesis is that dysregulated fuel metabolism is a major driver of diabetic nephropathy. We propose that the beneficial effect of SGLT-2i in DN is related to changes in fuel metabolism. Our anticipated outcomes include reversal of many of the metabolomics findings reported in DN. We expect decreased fasting glucose and elevated serum ketones, as previously reported. We also predict reductions in the levels of short-chain acyl-carnitines, increased C4-OH and long-chain acyl-carnitines as well as reductions in urinary organic acid excretion. Unfortunately, the scope of this proposal is too short to expect significant changes in albuminuria, although this will be assessed. If completed successfully, this project will help to link changes in mitochondrial fuel metabolism with the beneficial effects of the SGLT-2i class of drugs.

Our goals are to better understand the contribution of fuel metabolism to the development of DN, and to determine if changes to fuel metabolism can have a positive impact on this disease.

## **1.1 General Introduction**

Empagliflozin is a SGLT-2 inhibitor which is indicated as an adjunct to diet and exercise to improve glycemic control in adults with type 2 diabetes mellitus, and to reduce the risk of cardiovascular death in adult patients with type 2 diabetes mellitus and established cardiovascular disease. By inhibiting sodium-glucose co-transporter 2 (SGLT2), the predominant transporter responsible for reabsorption of glucose from the glomerular filtrate back into the circulation, empagliflozin reduces renal reabsorption of filtered glucose, thereby increasing urinary glucose excretion. Presently empagliflozin is not indicated for the treatment of diabetic nephropathy (DN), although it has been shown in previous studies to have a beneficial effect on DN.

## **1.2 Rationale and Justification for the Study**

We hypothesize that treatment with empagliflozin taken orally at 10mg per day for 30 days will lead to significant changes in the circulating metabolomics pattern in patients with DN.

Since we are interested in understanding the metabolic effects of the drug, we propose to administer the drug for a period of 30 days. We will perform a comprehensive analysis of the state of fuel metabolism in these patients before, during and after the administration of empagliflozin using targeted metabolomics and other approaches. Our goal is to discover key changes in fuel metabolism in DN patients receiving empagliflozin.

### **1.2.1 Rationale for the Study Purpose**

Clinical trials of SGLT-2i in patients with type 2 diabetes (T2DM) have shown unexpectedly strong effects of the drug on diabetes complications, including slowing the progression of DN. The mechanisms underlying the protective effect on renal complications of diabetes have not been fully elucidated.

Existing literature suggest that the forced excretion of glucose in the urine resulting from SGLT-2i use leads to unique physiologic changes, leading to a major shift in fuel metabolism away from glucose towards the burning of fat and ketone bodies. The shift in fuel metabolism is of particular interest given our recent findings of altered fuel metabolism in patients with diabetic nephropathy.

The aim of our study is to examine the state of fuel metabolism in patients with DN both before and after the use of SGLT-2i. If completed successfully, this study will help to link changes in mitochondrial fuel metabolism with the beneficial effects of the SGLT-2i class of drugs. A better understanding of the relationship between mitochondrial fuel metabolism, DN, and the metabolomic effects of SGLT-2i may point a way to more therapies for DN which target mitochondrial fuel metabolism.

### **1.2.2 Rationale for Doses Selected**

The dose of empagliflozin 10mg per day is selected as it is the recommended initiation dose according to the prescribing information provided by the manufacturers. The dose selection is similar to dosages used in patients in standard clinical practice and in large clinical trials.

### **1.2.3 Rationale for Study Population**

DN is the most common cause of end-stage renal disease (ESRD) in the US and also accounts for nearly

half of all new patients starting dialysis in Singapore, the highest in the Asia-Pacific region. ESRD is also a major cause of death, accounting for over 65% of deaths in T1DM patients with nephropathy and the 5-year survival rate being typically less than 10% in elderly patients with T2DM. Despite these sobering statistics, little progress has been made in early diagnostic markers or the availability of increased treatment options for the clinical management of DN. Current mainstay of therapy relies on control of hyperglycemia and blood pressure and pharmacologic blockade of the renin-angiotensin system (RAS) with ACE inhibitors or angiotensin receptor blockers (ARBs). Despite these treatments, DN typically progresses over time. Finally, no new therapies for DN have been offered the past few years and to our knowledge, there are only a couple of ongoing clinical trials in the US for potential new treatments for DN (clinicaltrials.gov).

#### **1.2.4 Rationale for Study Design**

We will conduct a single-arm open-label intervention study to examine the effects of a standard dose of empagliflozin on fuel oxidation patterns in patients with type 2 diabetes and DN. No randomization or blinding will be performed as the response to empagliflozin is stereotypical and the measured parameters are objective and thus not subject to observer bias.

### **2 HYPOTHESIS AND OBJECTIVES**

#### **2.1 Hypothesis**

Our study hypothesis is that dysregulated mitochondrial fuel oxidation, as measured by changes in the circulating metabolomics pattern of DN patients, is a major driver of diabetic nephropathy. Furthermore, we hypothesize that treatment with empagliflozin over a period of 30 days will reverse the metabolomics changes seen in patients with DN.

#### **2.2 Primary Objectives**

The primary objective is to study the effects of empagliflozin on fuel metabolism patterns in patients with DN. We will conduct a single arm intervention study to examine the effects of a standard dose of empagliflozin on fuel oxidation patterns in patients with type 2 diabetes and DN. Since we are interested in understanding the metabolic effects of the drug, we propose to administer the drug for a period of 30 days. We will perform a comprehensive analysis of the state of fuel metabolism in these patients before and after the administration of empagliflozin using targeted metabolomics and other approaches. Our goal is to discover key changes in fuel metabolism in DN patients receiving empagliflozin.

#### **2.3 Secondary Objectives**

N.A.

#### **2.4 Potential Risks and Benefits:**

##### **2.4.1 Potential Risks**

###### *Venepuncture*

This study requires blood to be drawn from a vein in the arm. For most people, blood draws using needle punctures do not cause any serious problems. However, drawing blood may result in pain at the point of

puncture, a feeling of faintness, irritation of the vein and bruising or bleeding at the site of needle puncture. There is also a very slight possibility of an infection at needle puncture site. An experienced staff will perform these procedures and every precaution will be taken to prevent infection.

#### *Indirect calorimetry*

Indirect calorimetry involves the placement of a transparent plastic hood with ventilation over the head for 30-minute intervals during the 2nd and 3rd study visit. It is well tolerated but some people may feel claustrophobic. To avoid this, a brief trial run will be performed for subjects to familiarize with the equipment and measurement.

#### *Adverse Effects Related to empagliflozin*

##### A) Allergic Reactions

All drugs have a potential risk of an allergic reaction. Allergic reactions range from mild reactions such as skin itchiness, rash, eye swelling to more severe allergic reactions that affects the blood pressure (allergic anaphylaxis). Severe allergic reactions could become life threatening if not treated quickly.

##### B) Hypotension

Empagliflozin causes intravascular volume contraction. The incidence of symptomatic hypotension is greater in patients with renal impairment, elderly individuals, in patients with low systolic blood pressure, and patients on diuretics. Subjects will be advised to avoid prolonged periods of fasting or water deprivation. They will be advised to maintain an adequate intake of water especially during periods of greater insensible fluid loss (eg: exercise or hot weather). All subjects will be educated about signs and symptoms of hypotension. Individuals above age 65 years, or with more severe renal impairment will be excluded from this study.

##### C) Ketoacidosis

Reports of ketoacidosis, a serious condition requiring urgent hospitalization have been reported in patients taking empagliflozin. Some of these cases were identified in patients with type 1 diabetes, in whom empagliflozin is not indicated. We have excluded patients with type 1 diabetes from our study. In patients with T2DM receiving empagliflozin, the FDA identified potential triggering factors for ketoacidosis including intercurrent illness, reduced food and fluid intake due to illness or surgery, reduced insulin doses, history of alcohol intake, and pancreatic disorders suggesting insulin deficiency (eg: type 1 diabetes, history of pancreatitis, pancreatic surgery). All subjects will be assessed by a physician for factors that may predispose to ketoacidosis, including pancreatic insulin deficiency from any cause, caloric restriction, and alcohol abuse. Subjects in whom these factors are identified will be excluded from the study. All subjects will be educated to temporarily discontinue empagliflozin in situations known to predispose to ketoacidosis (eg: intercurrent illness, prolonged fasting due to acute illness or surgery), and how to identify symptoms suggestive of ketoacidosis and to seek medical attention. Subjects may contact the study team should they fall ill. The study team will advise patients regarding period of discontinuation of study drug, if applicable.

##### D) Acute kidney injury and impairment in renal function

Treatment with empagliflozin is known to cause an initial mild fall in eGFR which is related to one of its underlying mechanism of actions in altering tubuloglomerular feedback. This initial mild fall in eGFR is followed by a progressive recovery of GFR during the following weeks. Empagliflozin may also result in acute kidney injury or significantly increased serum creatinine as a result of intravascular volume contraction. Factors that may predispose to acute kidney injury include more severe renal impairment,

congestive heart failure, and some concomitant medications (including diuretics, ACE inhibitors, angiotensin receptor blockers, and NSAIDs). Subjects with more severe renal impairment will be excluded from this study. Subjects will be educated on situations that predispose to acute kidney injury, such as reduced oral intake or increased fluid losses, and to temporarily discontinue empagliflozin if these occur. All subjects will have their kidney function tested before and monitored during this study.

**E) Genital mycotic infections, urinary tract infections, urosepsis and pyelonephritis**

Treatment with SGLT-2i increases the risk for genital mycotic infections and urinary tract infections, which are usually mild. Serious urinary tract infections including urosepsis and pyelonephritis requiring hospitalization in patients receiving SGLT-2i have been described. Patients with a history of recurrent urinary tract or genital mycotic infections, and patients with a history of serious urinary tract infections will be excluded from this study.

**F) Fournier's gangrene**

On 29th August 2018, the U.S. Food and Drug Administration (FDA) warned that cases of a rare but serious infection of the genitals and area around the genitals have been reported with SGLT2 inhibitors. This serious rare infection, called necrotizing fasciitis of the perineum, is also referred to as Fournier's gangrene. In the five years from March 2013 to May 2018, 12 cases of Fournier's gangrene were identified in patients taking an SGLT2 inhibitor (7 men and 5 women), all of whom were hospitalized and required surgery. In 2017, an estimated 1.7 million patients received a dispensed prescription for an SGLT2 inhibitor from U.S. outpatient retail pharmacies. Fournier's gangrene developed within several months of the patients starting an SGLT2 inhibitor. In accordance with recommendations made by the U.S. FDA, patients will be counselled regarding the risk of Fournier's gangrene before commencing treatment with empagliflozin. Patients will be counselled to seek medical attention immediately if they experience any symptoms of tenderness, redness, or swelling of the genitals or the area from the genitals back to the rectum, and have a fever above 38.0 degrees Celsius, or a general feeling of being unwell.

**G) Hypoglycemia**

Treatment with empagliflozin is expected to result in a fall in blood glucose. Hypoglycemia is a potential side effect of all glucose-lowering medications, including empagliflozin. Patients who are at high risk of significant hypoglycaemia will be excluded from the study. Patients at high risk of significant hypoglycaemia include those with 1 or more episodes of severe hypoglycaemia in the last 1 year, and frequent (at least once a week) hypoglycaemia episodes of any severity.

***Issues Related to Pregnancy and Breast-Feeding***

There is inadequate data about the use of empagliflozin in pregnant or breast-feeding women. Therefore, pregnant or breast-feeding women cannot participate in this study. Sexually active women of childbearing potential must use a reliable method of birth control while participating in this study. Reliable methods of birth control are considered to be abstinence (not having sex), oral contraceptives (the pill), intrauterine device (IUD), DepoProvera, Norplant, tubal ligation (tubes tied) or vasectomy of the partner. An acceptable although less reliable method, involved the careful use of condoms and/or a spermicidal foam or gel along with a diaphragm, cervical cap, or sponge. Study subjects would be encouraged to discuss this issue further with their doctor if they any questions.

***Issues Related to Pediatric Use***

The safety and effectiveness of empagliflozin in pediatric patients under 18 years of age have not been established. Patients under 21 years of age will be excluded from this study.

## **2.4.2 Potential Benefits**

There is unlikely any direct benefit from participating in this study as treatment with empagliflozin for one month is unlikely to provide any long-term benefit. However, completion of the study will provide us with a better understanding of the relationship between empagliflozin use and mitochondrial fuel oxidation, and the biochemical changes surrounding the development of DN. The results of the study may point a way to more therapies for DN which target mitochondrial fuel metabolism.

## **3 STUDY POPULATION**

### **3.1 List The Number and Nature of Subjects to be Enrolled.**

Assuming that treatment with empagliflozin would result in a significant shift in metabolic fuel selection, 40 subjects with DN will be required. Assuming a screen failure rate of 1 in 3, a total of 60 subjects will need to be recruited from the Singapore General Hospital (SGH) Diabetes and Metabolism Centre (DMC) clinics. There are no subject restrictions based on race of the subject in this study.

### **3.2 Criteria for Recruitment and Recruitment Process**

This will be a single-centre study conducted in SGH. Subjects from this trial will be patients attending the Diabetes and Metabolism Centre (DMC) clinics. Physicians at the DMC can refer any interested and suitable patients to the study team.

The study team will provide additional details regarding this study to all interested patients and they will be scheduled for consent taking and screening visit at the SGH Clinical Trials Research Centre (CTRC).

### **3.3 Inclusion Criteria**

Subject must meet all of the inclusion criteria listed below to participate in this study:

1. Man or woman between 21 and 65 years of age
2. Type 2 diabetes mellitus as defined by:
  - Fasting plasma glucose  $\geq 7.0\text{ mmol/l}$ , or
  - Symptoms of hyperglycemia with casual plasma glucose  $\geq 11.1\text{ mmol/L}$ , or
  - 2-hour plasma glucose  $\geq 11.1\text{ mmol/l}$  after a 75-gram oral glucose load, or
  - Known type 2 diabetes mellitus diagnosed by a medical practitioner
3. Two or more measurements indicating increased urine protein excretion within 1-year

Increased urine protein excretion is defined as:

- Urine microalbumin/creatinine ratio (ACR)  $> 3.3\text{ mg/mmol}$  creatinine or
- Urine total protein/creatinine ratio (PCR)  $> 0.2\text{ g/urine}$  creatinine

4. Known diabetes duration  $> 3$  months
5. HbA1c 7.5 – 9% (within 3 months prior to enrolment)
6. Not currently treated with an SGLT-2 inhibitor, and have not received SGLT-2 inhibitor therapy within the last 10 weeks.
7. Stable diabetes therapy for at least 3months as defined as:
  - No change in dose of diabetes medications by more than two-fold or
  - No new agents added within the previous 3 months
8. Stable doses of angiotensin converting enzyme (ACE) inhibitors or angiotensin AT(1)-receptor blockers (ARBs) for at least 3 months.
9. Capable of providing informed consent

Subjects with HbA1C between 7.5 – 9% will be recruited because treatment with SGLT-2i is indicated in these patients according to local clinical practice guidelines. Subjects with HbA1C  $> 9\%$  will be excluded due to safety considerations from uncontrolled hyperglycemia. We will exclude subjects on insulin treatment as insulin treatment may interfere with measured parameters.

We will not be studying children, or adults above the age of 65. The risk of drug related adverse effects increases in the elderly. All methods of contraception are allowed in women of childbearing age.

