#### 4.3 Study Visits and Procedures

**4.3.1** Patients who meet inclusion criteria and do not meet any of the exclusion criteria will be invited to participate during their visit to the DMC at SGH by the PI, Co-Is or their managing physician. Interested patients will be scheduled for their first study visit (**Visit 1**) within **28 days** at SGH CTRC.

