### **9.2 Statistical and Analytical Plans**

For the measurement of metabolic fuel utilization and related parameters at baseline and post-treatment, values will be compared using the paired Student's *t*-test. If the data are not normally distributed, the appropriate transformation will be used or a non-parametric approach will be considered. Hypotheses testing will be non-directional (two sided), with values < 0.05 as significance. Software programs SPSS (version 21; SPSS, Chicago, IL) and GraphPad Prism (version 6, GraphPad Software) will be used for all statistical analysis. There will be no planned interim analyses.

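### Inclusion criterion 7 joins its two stability conditions with *or*, so a patient whose diabetes-drug dose has recently changed more than two-fold still counts as stable

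*Protocol*

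**What the plan says.** Protocol section 3.3, item 7, opens with "Stable diabetes therapy for at least 3months as defined as" and then gives two bullets as the definition: "No change in dose of diabetes medications by more than two-fold or" and "No new agents added within the previous 3 months". The first bullet has no time window of its own, so its 3 months come from the lead-in.

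The design is stated in section 1.2.4: "We will conduct a single-arm open-label intervention study to examine the effects of a standard dose of empagliflozin on fuel oxidation patterns". Section 9.2 gives the analysis: for "parameters at baseline and post-treatment, values will be compared using the paired" t-test, two-sided at 0.05, with a transformation or non-parametric method if the data are not normal. Table 1 places metabolomic profiling, fasting glucose and indirect calorimetry at Visits 2 and 3, so Visit 2 is the baseline for these measurements.

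**The concern.** Two separately negated statements joined by *or* make a definition that either one satisfies. The lead-in asks for stable therapy, but the definition admits patients whose therapy has just changed substantially.

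This matters more here than in a randomised trial. With no control group, nothing absorbs a change in background glucose-lowering therapy that is still taking effect between baseline and the final visit. In the paired comparison over all subjects it adds to, or masks, the effect attributed to empagliflozin. Item 7 is the entry rule meant to limit this. The protocol already treats background therapy as a possible source of interference, since section 3.3 excludes insulin users for that reason.

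**Working it through.** **1. The logic of the definition.** Let A be no dose change of more than two-fold, and B no new agent, both over 3 months.

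| Patient | A | B | A or B (as written) | A and B |
|---|---|---|---|---|
| No large dose change, no new agent | yes | yes | stable | stable |
| Large dose change, no new agent | no | yes | stable | not stable |
| New agent, other doses unchanged | yes | no | stable | not stable |
| Both changes | no | no | not stable | not stable |

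As written, 3 of the 4 states pass. With both conditions required, 1 of 4 passes. The second row is the clear conflict with the lead-in. The third is a conflict unless starting a drug is itself read as a dose change of more than two-fold.

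**2. Whether other text settles the reading.**
- Items 2 and 3 of section 3.3 use *or* between bullets for true alternatives, which favours the literal reading.
- Item 6 joins two required conditions with *and*: "Not currently treated with an SGLT-2 inhibitor, and have not received SGLT-2 inhibitor therapy within the last 10 weeks".
- Item 8 points the other way: in "Stable doses of angiotensin converting enzyme (ACE) inhibitors or angiotensin AT(1)-receptor blockers (ARBs) for at least 3 months" the *or* would cover both drugs for a patient who takes both.
- The rule that every inclusion criterion must be met governs the numbered items, not the bullets inside one.
- The exclusions in 3.4 bar insulin, anti-obesity drugs and systemic glucocorticoids, and item 6 covers SGLT-2 inhibitors. Nothing bars a recent change in another glucose-lowering drug. Section 6.6 only records concomitant drugs.

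**3. Whether the visit windows leave room for drift.** Inputs: section 4.3.1, "Interested patients will be scheduled for their first study visit" within 28 days of invitation; section 4.3.3, Visit 2 within 14 days of Visit 1; section 4.3.4, Visit 3 at 30 ± 7 days, that is 23 to 37 days, after Visit 2. I take 3 months as 90 days.

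For a change x days before Visit 1:
- Visit 2 falls x to x + 14 days after the change.
- Visit 3 falls x + 23 to x + 51 days after it (0 + 23 and 14 + 37).
- Both visits are inside 90 days on every permitted schedule if x ≤ 90 − 51 = 39.
- Visit 3 can be inside 90 days only if x ≤ 90 − 23 = 67. For x from 40 to 67 it depends on the schedule.

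For a change made at the invitation visit, x is 0 to 28. Visit 2 is then 0 to 28 + 14 = 42 days after it, and Visit 3 is 23 to 28 + 51 = 79 days after it. Both always lie inside the 3 months.

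**4. Illustration of the effect on the test.** The affected share and the drift are assumptions; the protocol gives neither. Take n = 40 paired differences with SD 1 and no drug effect. Each subject drifts by d SD with probability p, and a fraction q of those who drift go the opposite way. The mean shift is m = p·d·(1 − 2q), the variance is 1 + p·d² − m², and the noncentrality is √40·m/√variance. For p = 0.20, d = 1, q = 0: m = 0.20, variance = 1 + 0.20 − 0.04 = 1.16, noncentrality = 6.325 × 0.20/1.077 = 1.17. Simulated two-sided type I error (400,000 trials per cell):

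| Direction of drift | d | p = 5% | p = 10% | p = 20% |
|---|---|---|---|---|
| All the same | 0.5 | 5.3% | 6.1% | 9.3% |
| All the same | 1.0 | 6.0% | 8.9% | 20.5% |
| One quarter opposite | 0.5 | 5.0% | 5.3% | 6.0% |
| One quarter opposite | 1.0 | 5.2% | 6.0% | 8.7% |
| Half opposite | 0.5 or 1.0 | about 5% | about 5% | about 5% |

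**The case against.** The strongest reply is that this is a drafting slip. The lead-in states the requirement, *no X or Y* is common loose English for neither, and at a single centre the study team reviews each patient's eligibility. Nothing shows that anyone would apply the loose reading. That stands as an argument about weight. It does not remove the contradiction, because *No* is repeated in each bullet and no other text requires both.

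Second, drug history is taken at Visits 1 and 3 and all medications are recorded, so affected subjects could be set aside in a sensitivity analysis. This also stands: the confounding applies to the paired test over all subjects, and the records offer a partial remedy.

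Third, visits falling inside 90 days do not show that a therapy change is still acting on acyl-carnitines, organic acids or calorimetry, and the protocol gives no time course for any background drug. That is right. The timing shows opportunity only, judged by the 3-month window that the criterion itself chose.

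Fourth, the error rates rest on assumed shares and drifts. The 20.5% needs one subject in five affected, each by a full SD in the same direction. They show how the size of the problem depends on those assumptions and are not an estimate for this trial.

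**Conclusion.** The point holds. Item 7 is wrong as written: its definition of stability admits patients whom its lead-in rules out, and no other criterion closes the gap for glucose-lowering drugs other than insulin and SGLT-2 inhibitors. It is an operative entry rule in a design with no control arm.

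The severity is minor. The likely intent is that both conditions hold, and staff may already apply it that way. The actual bias cannot be quantified from the protocol. Under the illustrative assumptions it ranges from nothing, when drifts balance, to a clear excess of false positives, when many subjects drift strongly in one direction. The timing result rests on 3 months being 90 days.

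**What to change.** In section 3.3, item 7, replace *or* with *and*, so that both conditions must hold over the 3 months already stated. This adds no new threshold and no data collection.

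If subjects are already enrolled, use the drug history taken at Visit 1 to identify those whose diabetes therapy changed in the 3 months before entry.

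**Cost.** One word in an amendment, and nothing further if staff already require both conditions. Otherwise some patients are lost to screening. If 5%, 10% or 20% of otherwise eligible patients (assumed shares) qualify only through the literal reading, the planned 60 screened for 40 subjects becomes 60/0.95 = 63.2, 60/0.90 = 66.7 or 60/0.80 = 75, that is about 64, 67 or 75. This assumes that the planned failure rate of 1 in 3 does not already count them and that they are found only at screening. Section 4.3.1 has criteria considered before invitation, so the increase could be zero.

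**What remains.** Dose changes of up to two-fold stay permitted, and the single-arm design stays open to other drift. The change reduces the problem without removing it.

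### Inclusion criterion 7 accepts a dose doubled or halved in the previous 3 months as stable therapy, so drift from that change can be counted as empagliflozin effect in an uncontrolled before-after test

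*Protocol*

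**What the plan says.** Protocol 3.3, item 7, opens with "Stable diabetes therapy for at least 3months as defined as" and then gives two bullets joined by *or*: "No change in dose of diabetes medications by more than two-fold" and "No new agents added within the previous 3 months". Item 8 asks for "Stable doses of angiotensin converting enzyme (ACE) inhibitors or angiotensin AT(1)-receptor blockers (ARBs) for at least 3 months" and does not define stable.

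Section 1.2.4 describes the design: "We will conduct a single-arm open-label intervention study to examine the effects of a standard dose of empagliflozin". Section 9.2 states the analysis: for baseline and post-treatment measurements, "values will be compared using the paired Student's" *t*-test, and "Hypotheses testing will be non-directional (two sided), with values < 0.05 as significance".

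On timing, Table 1 lists the eligibility check at Visit 1 only, and drug history at Visits 1 and 3. Visit 1 falls within 28 days of invitation (4.3.1). Visit 2, the metabolic baseline and first dose, follows within 14 days (4.3.3). Visit 3 is 30 ± 7 days later (4.3.4). Section 6.6 has concomitant medication documented. The protocol states no run-in and does not fix background doses between the visits.

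**The concern.** A stability criterion in a before-after study is there so that the background is flat between the two measurements. Item 7 does not secure that. A dose that was doubled or halved shortly before Visit 1 meets the first bullet on its own terms, and the *or* opens a second route in.

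No concurrent control subtracts whatever else is changing over the same month. If glucose or fuel measures are still settling at Visit 2, the rest of that settling falls inside the Visit 2 to Visit 3 difference, and the paired test attributes it to empagliflozin. The direction can matter. The study aims in section 1 predict a fall in fasting glucose on the drug, and residual drift from an increase in background glucose-lowering therapy would look the same.

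The protocol accepts the principle elsewhere in 3.3: insulin users are excluded because insulin may interfere with the measurements, and recent SGLT-2 inhibitor use within 10 weeks is barred. The argument in 4.1 that the measurements are objective answers observer bias. It does not answer a second treatment effect that is still developing.

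**Working it through.** **1. What item 7 admits.** Each case is read against the literal text.

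| Change in the last 3 months | Bullet 1 (dose) | Bullet 2 (agent added) | Joined by *or* | Joined by *and*, bullets unchanged |
|---|---|---|---|---|
| Dose doubled or halved, no agent added | met | met | eligible | eligible |
| Dose tripled, no agent added | not met | met | eligible | not eligible |
| Agent added, other doses unchanged | met | not met | eligible | not eligible |

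Changing *or* to *and* alone leaves the first row open. Rewording bullet 1 alone also leaves it open, because bullet 2 is still met. Both edits are needed. Treating a halving as a two-fold change is the natural reading, though the text does not spell it out.

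**2. The plan's own figure.** Section 9.1: 40 subjects with a screen failure rate of 1 in 3 gives 40 / (1 − 1/3) = 60 screened, as stated. The 40 itself cannot be reproduced, because no effect size, SD or power is given. For scale, a paired *t*-test with n = 40 and two-sided 0.05 has 80% power at a mean change of 0.454 SD of the paired difference and 90% at 0.526 SD.

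**3. Size of the possible bias.** From the protocol: n = 40, two-sided alpha 0.05, paired *t*-test. Assumed, because the protocol gives no figure: a share f of subjects has residual drift, each by δ, in units of the SD of the paired difference without drift.

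- If all drift goes one way, the mean bias is f·δ.
- The SD of the mixed population is √(1 + f(1 − f)δ²).
- With no drug effect, the rejection rate comes from a noncentral *t* on 39 degrees of freedom with noncentrality √40 × (bias / SD) and critical value 2.023.

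Example, f = 30% and δ = 0.8: bias = 0.3 × 0.8 = 0.24. SD = √(1 + 0.21 × 0.64) = 1.065. Standardised shift = 0.24 / 1.065 = 0.225. Noncentrality = 6.325 × 0.225 = 1.43. Rejection rate = 0.285.

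| f | δ | Direction | Mean bias (SD) | Rejection rate, SD = 1 | Rejection rate, mixture SD |
|---|---|---|---|---|---|
| 10% | 0.25 | one way | 0.025 | 0.053 | 0.053 |
| 10% | 0.5 | one way | 0.05 | 0.061 | 0.061 |
| 20% | 0.8 | one way | 0.16 | 0.167 | 0.156 |
| 30% | 0.8 | one way | 0.24 | 0.316 | 0.285 |
| 30% | 0.8 | two-thirds up, one-third down | 0.08 | 0.078 | 0.074 |
| 30% | 0.8 | half and half | 0 | 0.05 | about 0.05 |

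For the two-to-one row: bias = 0.2 × 0.8 − 0.1 × 0.8 = 0.08, SD = √(1 + 0.3 × 0.64 − 0.08²) = 1.089.

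**4. If no subject has residual drift (f = 0),** bias from this source is 0 and the error rate is the nominal 0.05. The screening arithmetic does not change unless screen failures rise above 1 in 3.

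**The case against.** The strongest reply is that the protocol defines stable openly and that where to put the edge of a tolerance is a matter of choice. Moving it from more than two-fold to two-fold or more still admits a 1.5-fold change. That is true: the fix narrows the gap and does not abolish it. The lead-in nevertheless promises 3 months of stable therapy, and a definition that accepts a doubling inside that window serves the promise poorly in a study with no control.

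Several further readings are tempting, but the documents do not support them:

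- **That bias does enter.** It arises only if recently titrated patients are enrolled and are still drifting at Visit 2. The protocol says neither. Up to 28 days may pass before Visit 1 and up to 14 more before Visit 2, which gives some time to settle. These are maximum intervals, so they reduce the problem without removing it.
- **That the error rate is about 30%.** That figure needs 30% of subjects drifting by 0.8 SD in one direction. A drift of 0.8 SD per affected subject exceeds the 0.454 SD mean change detectable with 80% power, and mixed directions largely cancel.
- **That item 8 allows no tolerance and so shows a stricter standard.** Item 8 leaves stable undefined, so the contrast rests on silence.
- **That stopped agents are plainly missed.** Stopping an agent takes its dose to zero, which bullet 1 can be read to cover as a reduction of more than two-fold. Naming it is a clarification.

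It also stands that medication is recorded, so recently titrated patients could be identified and examined in a sensitivity analysis. Such an analysis may sit in an analysis plan not seen here. It would help, but with 40 subjects and no control it is a weaker remedy than a tighter entry rule.

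**Conclusion.** The point holds as a possible bias. Item 7 counts an exact doubling or halving in the previous 3 months as stable, and its *or* lets a patient in on one bullet alone. The single-arm paired comparison cannot separate residual drift from the effect of empagliflozin.

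The size is unknown. Under the assumed values above, the nominal 5% error ranges from about 5% (small drift, or drift evenly mixed in direction) to about 30% (30% of subjects, 0.8 SD, all one way). With a real drug effect, the estimate shifts by the same mean bias, upward or downward according to the direction of the drift. The wording of item 7 is certain. The share of patients, the amount of drift and its direction are assumptions.

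**What to change.** Amend Protocol 3.3, item 7, in three places:

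1. Join the bullets with *and*, so that both must be met. Without this, the next edit has no effect, because a doubled dose still qualifies through the second bullet.
2. Reword the first bullet so that a dose change of two-fold or more in the 3 months before Visit 1 does not count as stable.
3. Reword the second bullet to say that no diabetes agent was added or stopped in the same 3 months.

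Allow rescreening once 3 months have passed since the change. These edits define eligibility for the comparison and set no one's treatment.

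The cost is a few words. Some recently titrated patients will enter later or not at all, so the assumed screen failure rate of 1 in 3, and with it the 60 to be screened, should be checked against the tighter rule.
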